17.1.3. Serious Adverse Event

An SAE is any untoward medical occurrence that at any dose; results in death, is life-threatening, requires inpatient hospitalization or prolongation of existing hospitalization, results in persistent or significant disability/incapacity, or is a congenital anomaly/birth defect. Important medical events that may not result in death, be life-threatening, or require hospitalization may be considered serious when, based upon appropriate medical judgment, they may jeopardize the patient or subject and may require medical or surgical intervention to prevent one of the outcomes listed in this definition. Hospitalization means the participant has been formally admitted to a hospital for medical reasons. It does not include a presentation at a casualty or emergency room. Hospitalization for elective treatment of a pre-existing condition that did not worsen during the study is not considered an SAE or AE. Complications that occur during hospitalization are AEs. If a complication prolongs hospitalization or otherwise meets seriousness criteria, the event is an SAE.

17.1.4. Intensity/Severity of an AESI/SAE

All AESI/SAEs will be graded as mild, moderate, or severe by the investigator based on her/his medical judgment and the following guidance:

- **Mild:** asymptomatic or mild symptoms; clinical or diagnostic observations only; intervention not indicated.
- **Moderate:** limiting age-appropriate instrumental activities of daily living (e.g. preparing meals, shopping for groceries or clothes, using the telephone). Minimal, local or non-invasive intervention indicated.
- **Severe:** Medically-significant but not immediately life-threatening; disabling; limiting self-care activities of daily living (e.g. bathing, dressing and undressing, feeding self); hospitalization or prolongation of hospitalization indicated.

17.1.5. Relationship to the Trial Medication

All AESIs/SAEs will be assessed for causal relationship to the study medication by the investigator and reported as either definitely, probably, possibly, unlikely related, or not related.

17.1.6. Serious Unexpected Suspected Adverse Reaction

A suspected unexpected serious adverse reaction (SUSAR) is a suspected adverse reaction related to an investigational medicinal product that is both unexpected and serious. An SAE will be considered unexpected if the nature, severity, or frequency of the event is not consistent with the information previously described for the trial medication in the Investigator Brochure (IB).

17.2. Safety Reporting

17.2.1. AESI/SAE Data Collection & Follow-Up Period

AESI/SAE data will be collected and followed-up from the time signed informed consent is obtained and up to the Week 16 EOT visit for the double-blind period. Follow-up information on ongoing AESIs/SAEs obtained after the participant's respective EOT visit (as applies) will not be collected in the eCRF but all attempts will be made to follow-up SAEs/AESIs until they have resolved or stabilised.

17.2.2. Trial Investigator Responsibilities in Reporting AESIs/SAEs

Regardless of the suspected causality, every AESI/SAE must be reported by the site investigators as per the local regulatory and ethical requirements. All SAEs should be reported by completing the paper (Council for International Organizations of Medical Sciences [CIOMS] or relevant form) and eCRF SAE Form. The reports should identify participants by unique identification numbers assigned to the trial participants. SAEs should be promptly reported to the concerned parties and followed-up until resolution as per the local ethical and regulatory requirements. The Investigator should supply additional information (e.g. laboratory results, specialist/hospital letters, and autopsy results, etc.) if required by the CRO. Investigators are responsible for assessing if an AE meets the criteria for reporting as serious, the intensity of the event, and the relationship of the event with the trial medication.

17.2.3. Reporting of AESIs & SAEs

At each trial scheduled visit and unscheduled visits during the trial, site staff will ask participants about the incidence of any AESIs or SAEs since the previous visit. Other AEs will not be recorded since these drugs are well-known and established with widespread use. Site staff may also become aware of the incidence of AEs during a phone call with participants. All SAEs that site staff becomes aware of from the time informed consent is obtained until 30 days after discontinuation of the trial medication must be recorded. The following information will be collected for each AESI and SAE: event name, date of onset, severity, a possible cause of the event, relationship to trial medication, action taken regarding the trial medication, treatment given to manage the event (if applicable), the outcome of event, and date of resolution (if applicable).

An increase in the severity of a previously reported AESI or SAE during the trial will be reported as a new AESI or SAE with higher severity. A decrease in the severity of a previously reported AESI or SAE during the trial, will not require changes to the reported severity. Worsening of a condition, recurrent episodes, and further complications if any are to be reported as a follow-up of the original event.

All SAEs will be reported by the site staff to the sponsor via the eCRF within 24-hours of first becoming aware

of the event. Additional information will be collected including, seriousness criteria, hospitalization date and discharge (if applicable), and procedures performed (if applicable).

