3.11.1.2 Adverse Event Summaries

For the summary of safety parameters, AEs will be classified according to the treatment period and treatment received as of the start date of the AE (Section 3.5.3). If an AE is ongoing at the time of randomization, it will be allocated to the Period 1 treatment. If a treatment ongoing at randomization worsens following randomization, the AE worsening will be allocated to the Period 2 treatment.

AESIs and SAEs will be classified according to the MedDRA (Medical Dictionary for Regulatory Activities) system (version 24.0, March 2021) and summarized by system organ class and preferred term.

Treatment periods for AE summary include: Period 1, Period 2, Period 3, Randomization Period, and Period 4. The total number of events and incidence of participants experiencing AESIs will be tabulated by treatment group and overall for the specified study periods.

For each period, any AESI or SAEs that emerges or worsens during the period of interest will be summarized:

- Adverse Events of Special Interest,
- Serious AE,
- Related AESIs defined as those judged by the investigator to be 'possibly', 'probably' or 'definitely' related
- Related SAEs defined as those judged by the investigator to be 'possibly', 'probably' or 'definitely' related,
- AE leading to trial medication discontinuation
- AE leading to trial discontinuation defined as a request by the participant to withdraw from future follow-up visits

AESIs of abnormality detected in laboratory assessments for Period 1 will only include those whose lab value for that parameter was in the normal range at baseline. Summaries of AESI and SAEs occurring during the Randomized Period will include risk differences with 95% CI, computed using the Newcombe hybrid score method (with continuity correction; https://pubmed.ncbi.nlm.nih.gov/21996567/), to evaluate GMRx2 against each dual control treatment group and overall. System organ classes and preferred terms with events occurring in at least 1% of the sample will be included.

In addition, the frequency and percentage of participants discontinuing treatment due to an AE will be reported with risk differences between treatment groups computed using the Newcombe hybrid score method (with continuity correction) to evaluate the primary safety endpoint among GMRx2 treatment participants compared to each dual control treatment group, and overall.

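### The SAP has no rule for a same-grade recurrence that the protocol files under an earlier event, and its AESI definition omits headache

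*Protocol*

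**What the plan says.** **Reporting by sites.** Protocol 17.2.3 has two sentences on later changes in an event already reported. One says "An increase in the severity of a previously reported AESI or SAE during the trial will be reported as a new AESI or SAE", at the higher severity. The other says "Worsening of a condition, recurrent episodes, and further complications if any are to be reported as a follow-up of the original event". On what is recorded, the same section says "The following information will be collected for each AESI and SAE: event name, date of onset, severity", and the list goes on to a single date of resolution. No date of recurrence is listed.

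**Allocation in the analysis.** SAP 3.11.1.2 says "AEs will be classified according to the treatment period and treatment received as of the start date of the AE". Two sentences deal with events that straddle randomization: "If an AE is ongoing at the time of randomization, it will be allocated to the Period 1 treatment", and "If a treatment ongoing at randomization worsens following randomization, the AE worsening will be allocated to the Period 2 treatment". For the period tables, "any AESI or SAEs that emerges or worsens during the period of interest will be summarized". On counts, "The total number of events and incidence of participants experiencing AESIs will be tabulated" by treatment group and study period.

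**AESI definition.** Protocol 17.1.2 lists symptoms possibly related to hypotension, abnormal results for named laboratory tests, headache, peripheral edema, and any other symptom or laboratory abnormality that led to permanent discontinuation. SAP 3.11.1.1 has the hypotension, laboratory and withdrawal items. It has no headache item, and in place of peripheral edema it has pedal edema as a participant-reported symptom.

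**The concern.** A recurrence filed as follow-up sits under the original event. If that event's start date decides the period, the recurrence is credited to the period of the first episode and not to the one in which it happened. Every participant takes GMRx2 Dose 2 during run-in (Protocol 8.4.1) and AESIs are collected from consent (Protocol 17.2.1), so a randomized participant can bring in a run-in event. The SAP expects this, since it has a rule for events ongoing at randomization.

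At stake are outcomes that count participants with an event from randomization onward, above all symptomatic hypotension to Week 6 and to Week 12 (Protocol 9.2.2). A participant whose only episode after randomization is a same-grade recurrence of a run-in episode could be tabulated as having had none.

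The two AESI lists raise a separate problem. If the SAP definition is used to select events for the AESI tables, headaches that sites recorded under the protocol, and that did not lead to withdrawal, fall outside it.

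**Working it through.** The plan states no figure on this point, and the documents give no recurrence rate. The check therefore sets the rules side by side.

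| Later episode | Protocol 17.2.3 | SAP 3.11.1.2 | Result |
|---|---|---|---|
| Run-in event, resolved, recurs after randomization at a **higher** grade | New event by the severity sentence; follow-up if read as worsening | Own start date, or counted as worsening | Covered, provided the record is dated |
| Run-in event, resolved, recurs after randomization at the **same** grade | Follow-up of the original | No rule; original start date lies in Period 1 | Can be counted in Period 1 only |
| Run-in event ongoing and unchanged at randomization | Same record | Period 1 by express rule | Intended; not in dispute |
| Period 2 event recurs at the same grade in Period 3 | Follow-up of the original | No rule; original start date lies in Period 2 | Can be absent from the Period 3 tables |

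**Step 1: the two protocol sentences.** They fit together only if worsening of a condition means a change without a change of grade. The protocol does not say so. The SAP's worsening rule also needs the worsening to have a dated record.

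**Step 2: which outcomes the second row reaches.** A recurrence in Period 2 can be missed in symptomatic hypotension to Week 6 and to Week 12. A first recurrence in Period 3 can be missed only to Week 12. In both cases the participant must have no other qualifying episode in the interval.

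**Step 3: SAEs.** The same logic applies, but the path is very narrow. The participant must have an SAE in run-in, still have tolerated run-in medication (Protocol 8.2.1), pass the safety exclusions at randomization (Protocol 8.2.2), and then have a same-grade recurrence as the only SAE after randomization.

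**Step 4: the fourth row.** The participant already counts in the outcomes to Week 6 and to Week 12 through the Period 2 episode. No named safety outcome covers Week 6 to Week 12 alone. Only the descriptive Period 3 tables and the event totals change.

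**Step 5: what is not reached.** The sodium, potassium and eGFR outcomes come from scheduled laboratory values (SAP 3.11.2), and the orthostatic outcomes from clinic readings (SAP 3.10.3.2). Neither depends on adverse event start dates.

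**Step 6: headache.** Under SAP 3.11.1.1 a non-serious headache is an AESI only through the item on symptoms that led to treatment withdrawal, unless the investigator thought it possibly related to hypotension. Under Protocol 17.1.2 it is an AESI in its own right. No outcome in Protocol 9.2 names headache or edema.

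**The case against.** The strongest reply is that the loss is inferred. Protocol 17.2.3 tells sites how to link reports; it does not say that a recurrence goes undated or uncounted. The eCRF follow-up form is not in the documents and may hold a date for each episode. The SAP's word 'emerges' could be read to include a recurrence. For SAEs, Protocol 17.2.3 also has hospitalization and discharge dates collected where applicable, which could place a later admission in time. All of this stands. A reader might infer that recurrences will be lost; the documents show only that the written rules allow it and that no rule prevents it. They do not remove the gap either: a SAP should say where a foreseeable kind of event is counted, and this one leaves it to the programmer's reading.

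On headache, the reply is that sites collect by the protocol list and that SAP 3.11.1.2 summarizes AESIs by system organ class and preferred term, so recorded headaches may still appear, subject to the 1% display threshold. That also stands. A reader might infer that headache data are not collected or will be dropped; the documents do not support that. What remains is two definitions of AESI that disagree, with an effect on AESI incidence if the SAP's definition selects the events.

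**Conclusion.** The point holds and is minor. Two stated rules, read together, can place a same-grade recurrence after randomization in Period 1, and the SAP gives no rule to the contrary. The outcomes within reach are symptomatic hypotension to Week 6 and Week 12 and, by a very narrow path, SAEs to the same times. The AESI mismatch is a plain inconsistency that bears on AESI incidence only.

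The size cannot be determined from the documents. It depends on how many randomized participants had a resolved run-in event that recurred at the same grade as their only later episode, and on whether follow-up entries are dated. Having to tolerate run-in limits the number.

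Three stronger readings are tempting and unsupported:

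- **That the gap favours GMRx2.** Within an arm a missed recurrence is an undercount, but nothing in the documents says in which arm recurrences would be more frequent.
- **That it distorts the named outcomes through Period 3.** Protocol 7.1 does use the two double-blind periods to assess Dose 2 and Dose 3 in turn, but a recurrence from Period 2 to Period 3 changes descriptive tables and event totals only.
- **That it reaches the primary safety outcome.** That outcome counts participants who discontinued medication because of an adverse event between randomization and Week 12. Its own wording sets the timing, and it does not depend on how a recurrence is filed.

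**What to change.** - **SAP 3.11.1.2, counting rule.** Add: 'A recurrence or worsening recorded as follow-up of an earlier event is counted in the period in which that episode began.' Use the dates in follow-up records where they exist, and report the number of follow-up entries without a date.
- **SAP 3.11.1.2, wording.** In the sentence on worsening after randomization, replace 'a treatment ongoing' with 'an AE ongoing'.
- **SAP 3.11.1.1.** Use the AESI list of Protocol 17.1.2, with headache included and edema worded as in the protocol.
- **Protocol 17.2.3.** Reconcile the sentence on increased severity with the one on worsening and recurrence, if it is not too late. SAP 2.6.1 records that recruitment had already been terminated, so a protocol change may come after most or all of the data.

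The cost is a few lines of SAP text and one programming rule, with no added visits or data collection. If follow-up entries turn out to have no dates, the rule cannot recover those recurrences; the count of undated entries would then show how many events are in doubt.

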17.2.4. Reporting of SUSARs

The Medical Monitor assigned by George Clinical Safety will assess all suspected serious adverse reactions in order to determine expectedness in accordance with the known adverse effects of each investigational drug as listed in the IB. If a suspected serious adverse reaction is determined to be unexpected i.e. a SUSAR, the CRO will report to the applicable regulatory authorities within the required timelines. Follow-up reports will be generated in accordance with applicable regulatory requirements. Reports will also be provided to the overseeing IRB/IEC and Investigators as per country requirements.

17.2.5. Reporting of Pregnancy

Any occurrence of pregnancy in a trial participant during the trial from the time to signing the informed consent until 30 days after discontinuation of the trial medication will be reported by the site staff, using a pregnancy form, to the trial sponsor within 24 hours of the site staff first becoming aware of it. Pregnancy will be followed until final resolution (i.e., delivery or early termination). Congenital abnormalities/birth defects and spontaneous miscarriages should be reported and handled as SAEs. Elective abortions without complications should not be handled as AEs.

17.2.6. Reporting of Trial Medication Use Errors or Misuse

Reports of trial medication overdose, abuse, off-label use, misuse, or any other medication error should only be reported as an SAE if they are associated with suspected adverse drug reactions. Medication error refers to any unintentional error in the prescribing, dispensing, or administration of a medicinal product while in the control of the healthcare professional or participant. All trial medication overdose, misuse and other medication errors associated with suspected adverse drug reactions should be routinely followed-up to ensure that the information is as complete as possible with regards to the symptoms, treatments, outcomes, context of occurrence (e.g., error in prescription, administration, dispensing, dosage, etc.).

18. ETHICAL & REGULATORY COMPLIANCE

This trial will be designed, conducted, analyzed, and reported in compliance with ICH-GCP and local regulatory & ethical requirements.

18.1. Ethical Approval

All participating sites will submit to relevant IRB/IEC the trial protocol, PISCF and other trial-related essential documents, as required by the IRB/IEC, for review and approval. No sites will start the trial before the written approval of the IRB/IEC.

18.2. Regulatory Approval

Where applicable, the trial protocol, PISCF, and other trial-related essential documents will be submitted to the local regulatory agency as per the applicable requirement in the country.

18.3. Confidentiality

All documents and data relating to this trial are strictly confidential. Documents given to the investigators and trial sites by the CRO should not be disclosed to other parties without the written approval of the sponsor. The investigators/sites should maintain the confidentiality of the identification of all trial participants and assure the security and confidentiality of trial data and documents.

18.4. Protocol Amendments

Any change to the protocol will be made through a protocol amendment by the SC. The participating sites will submit the amendment to the relevant IRB/IEC, and the sponsor will submit to the regulatory agencies as per the local requirements.

18.5. Adherence to the Trial Protocol

Investigators/sites will adhere to the trial protocol, comply with the ethical and regulatory requirements for the conduct of the trial. Any deviations from the protocol must not be implemented unless such a deviation is required to prevent/eliminate immediate harm to the trial participant(s). The investigator/site will document protocol deviations along with reasons and notify them to the sponsor/CRO as per the local requirements.

19. ADMINISTRATIVE SECTION

19.1. Insurance

The sponsor provides insurance to cover medical expenses and/or pay compensation in the event of a trial-related injury or death to a trial participant and indemnify (with both legal and financial coverage) the investigator/site against claims arising from the trial, except in the case of claims that arise from malpractice and/or negligence, in compliance with local regulatory and ethical requirements.

19.2. Quality Assurance

Quality assurance will be achieved via compliance with relevant standard operating procedures, regulatory and ethical requirements; database design and data monitoring; training of all study staff on protocol and procedures; documentation of all procedures and processes; communication with stakeholders by the trial coordinating team; and direction and leadership of the trial by the SC.

19.3. Trial Documents Retention

All essential trial documents (as defined by ICH-GCP) will be archived and retained at the trial sites as long as to comply with the requirements of the sponsor (as specified in the agreement between the sponsor and the sites) and the national and international regulations (whichever is the longest period). At the end of such period, the investigator shall notify in writing to the sponsor of the intent to destroy all such documents. If the site investigator is unable to archive or cannot guarantee the archival requirements for some or all the documents, arrangements must be made between the investigator and the sponsor to store documents outside the site, in such a way that they can be accessed in the event of a regulatory inspection. These documents should not be destroyed without prior written approval from the sponsor. In the case of investigator wanting to assign the trial records to another party, or move them to another location, the sponsor must be notified in advance.

For sites using an electronic system to store trial participants medical records and it cannot be confirmed that the electronic system is validated (as per 21 Code of Federal Regulations Part 11 or equivalent standard) or the sponsor representatives or the regulatory inspectors cannot be provided access to the electronic system the site will be requested to print the source documents needed for verification. Such printed copies should be numbered, stapled, and should be certified by the site investigator that they are exact copies with the same information as in the original source record.

19.4. Ownership, Disclosure of Data and Dissemination policy

The Sponsor will have full ownership of the trial data. The sponsor will register the trial and post results on public platforms such as ClinicalTrials.gov within the timelines stipulated by the applicable IRBs/IECs and/or regulatory agencies. The sponsor will develop a clinical trial report documenting results that will be submitted to the regulatory agencies. The SC will be primarily responsible for publications arising from the trial, which will be submitted for presentations at conferences and publications in journals. Authorship on publications will be as per the International Committee of Journal Editors criteria. Draft publications should be shared with the Sponsor, who will provide any comments within 30 days of receipt.

